# b) PEP:

- i) Unknown or blinded medications for PEP: (CMDECOD 'BLINDED INVESTIGATIONAL DRUG' or 'UNKNOWN DRUG') and (CMTRT includes 'PEP' or 'POST EXPOSURE PROPHYLAXIS')
- ii) Include other known ARVs (where CMDECOD not 'BLINDED INVESTIGATIONAL DRUG' or 'UNKNOWN DRUG') excluding the following:
  - (1) F/TDFa 1
  - (2) generic F/TDF
  - (3) HIV vaccine
- iii) For HIV infected subjects, excludes HIV treatments starting on or after the date of HIV diagnosis

At any time that the medication start and end dates of F/TDF (or generic F/TDF) overlaps with the medication start and end dates of another ARV agent (excluding cabotegravir or HIV vaccine) by more than 1 day, that F/TDF (or generic F/TDF) record will be considered as treatment for PEP.

Each ARV agent can be matched to only 1 F/TDF (or generic F/TDF) record.

If the medication start and end dates exactly match between both F/TDF (or generic F/TDF) and another ARV agent, the record will be considered as treatment for PEP, including when the exact match is based on partial medication start and/or end dates of month/year only, year only, completely unknown dates or end date ongoing.

- 36) For the follow up time of HIV infections while on-treatment,
  - a) if the start date of any non-study PrEP treatment that includes the period after permanent discontinuation of study drug is incomplete, such instances should be queried. If incomplete start dates remain after query, the first of the month should be used for the start date of the non-study PrEP medication when determining on-treatment HIV infection events or on-treatment follow-up time.
  - b) if any non-study F/TDF for PrEP treatment that includes the period after permanent discontinuation of study drug overlaps with a 3rd ARV agent, the start date of non-study PrEP treatment will be used unless the start date of the 3rd ARV agent and non-study F/TDF is the same in which case the end date + 1 day of the 3rd ARV agent will be used as the start date for non-study F/TDF for PrEP treatment. Incomplete start and end dates should be queried. If incomplete end dates of the 3rd agent remain after query, the last day of the month should be used for the start date of the non-study PrEP medication when determining on-treatment HIV infection events or on-treatment follow-up time.
- 37) Subjects who received HIV vaccine will be identified through the Medical History eCRF verbatim terms (MHTERM) or the Non-Study ARV Medication eCRF drug name (CMTRTOT) containing both of the terms 'HIV' and 'vaccine'.

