### **Study Periods / Phases**

Subjects will be treated for at least 96 weeks during the blinded treatment phase. After completing the Week 96 visit, all subjects will continue to take their blinded study drug and attend visits every 12 weeks until the last subject reaches Week 96. All subjects will return to the study center for an End of Blinded Treatment Phase visit (may coincide with their next scheduled visit) upon notification by Gilead. Subjects who are still on study drug and subjects who have discontinued study drug due to HIV infection at the End of Blinded Treatment Phase visit will be offered entry into the 48 week OL phase of the study.

All subjects participating in the OL extension phase, without regard to their blinded treatment regimen, will be administered F/TAF QD and return for study visits at OL Weeks 12, 24, 36 and 48. HIV infected subjects may continue participation in the OL phase but will not be offered OL F/TAF.

In geographic regions where F/TAF is commercially available for PrEP, subjects will discontinue study drug at OL Week 48 and return 30 days later for a 30-Day Follow-Up visit. In geographic regions where F/TAF is not yet commercially available for PrEP, subjects will be given the option to continue receiving OL F/TAF beyond OL Week 48 and attend visits every 12 weeks until F/TAF becomes commercially available for use as PrEP, or until Gilead Sciences terminates the clinical development of F/TAF for PrEP (except in Denmark and the United Kingdom).

During the blinded treatment phase, subjects may choose to continue to participate in the study without taking study drug ("on-study, off-study drug"). Subjects who permanently discontinue study drug and continue to attend normal study visits (at minimum one visit at least 30 days after last dose) are not required to complete the follow-up visit. Any subject who has an Early Study Drug Discontinuation (ESDD) visit and who will not continue participating in the study, or any subject who will not continue participation in the OL phase of the study, must complete the 30-Day Follow-Up visit 30 days after the last dose of study drug.

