### 6.2.6. Sensitivity Analyses of the Secondary Efficacy Endpoint While On-Treatment (HIV Infection Rate Ratio Method)

A sensitivity analysis of the secondary endpoint will be based on HIV infections occurring while subjects are on-treatment during the double-blinded phase of the study using the PP analysis set. This on-treatment analysis will include HIV infection events and follow-up times occurring between first dose date to DB phase last dose date plus 10 days (for F/TDF) or plus 16 days (for F/TAF) and exclude:

- 1) HIV-1 infection events and follow-up time during the OLE phase.
- 2) Off study drug PrEP (off-treatment) HIV infection events and follow-up time defined as events and follow-up time occurring greater than 10 days for (F/TDF) or 16 days (for F/TAF) after permanent discontinuation of study drug (Appendix 7).
- 3) HIV infections and follow-up time occurring after subjects initiated any non-study PrEP treatment that includes the period after permanent discontinuation of study drug (including commercial drugs like Truvada®, generic Truvada, or investigational drugs like cabotegravir for PrEP with a stop date that is either ongoing or after permanent discontinuation of study drug).

The HIV infection incidence rate per 100 person-years of follow-up will be computed as the number of subjects with on-treatment HIV infection divided by the sum of all subjects' years (where a year is 365.25 days) of on-treatment follow-up while at risk of HIV infection in study. The duration of on-treatment follow-up while at risk of HIV infection is defined as the time between Day 1 (first dose date) and the end date (end date Day 1 date +1) where end date is defined as:

- For subjects who have been diagnosed as infected with HIV while on-treatment: the date of the on-treatment HIV infection which will be the date of the HIV infection diagnosis (as defined in Section 6.2.2).
- 2) For subjects who have not been infected with HIV while on-treatment, the earlier of:
  - a) last dose date + 10 days for F/TDF or + 16 days for F/TAF for subjects who permanently discontinued study drug (including subjects with off-treatment HIV infection)
  - date of last post-baseline HIV laboratory test (either local or Covance HIV laboratory tests, which may include the 30-day follow-up visit date) for subjects who have not permanently discontinued study drug

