### 7.6.4. PEP Medications While At Risk of HIV Infection During the Study

Post-exposure prophylaxis (PEP) is defined as treatment with any non-study drug ARV agent other than F/TDF (or generic F/TDF), cabotegravir or HIV vaccine while subjects are at risk of HIV infection as defined in Section 6.2.3.

The number of subjects with any PEP use and the number of PEP uses per subject while at risk of HIV infection during the DB phase, while on-treatment and while off-treatment and at risk of HIV infection will be summarized for the FAS.

The number of PEP uses per subject will be based on unique PEP medication start dates within each subject. Multiple ARV medications with overlapping start and end dates will be counted as only one PEP use. Consecutive PEP medications where the complete medication end date of one PEP medication differs from the complete medication start date of another PEP medication by one day or less will be counted as only one PEP use.

For PEP uses while at risk of HIV infection during the DB phase, if the start or stop date of the ARV medication is incomplete, the month and year (or year alone, if month is not recorded) of the start or stop date will be used to determine whether the ARVs occurred during the at risk of HIV infection period or not. The medication occurred during the at risk of HIV infection period if the month and year of the start or stop (or year of the start or stop, if month is not recorded) of the medication does not meet either of the following criteria:

- The month and year of start of the medication is after the date of the end of the at risk of HIV infection period
- The month and year of stop of the medication is on or before the date of the first dose of study drug

If the start and stop date of ARV medications are complete, the start date is not after the date of the end of the at risk of HIV infection period and the stop date is not on or before first dose date, or the ARV medications are marked as ongoing and start date is on or before the date of the end of the at risk of HIV infection period, the non-ARV medications are considered as occurring during the at risk of HIV infection period. Medications with completely missing start and end dates will not be considered as occurring while at risk of HIV infection during the study.

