    - If QSTEST 'Men Bottom [or Top] without condom last 90 days' is missing, but 'Men Bottom [or Top] last 90 days' 0 then summarize 'Men Bottom [or Top] without condom last 90 days' 0
  - b) Baseline CASI: Men Bottom [or Top] wo Condom since Screening
    - If QSTEST 'Men Bottom [or Top] wo Condom since Screening' is missing, but 'Men had Sex with since Screening' 0 then summarize 'Men Bottom [or Top] wo Condom since Screening' 0
  - c) Follow Up CASI:
    - If QSTEST 'Men Bottom [or Top] wo Condom since last visit' is missing, but 'Men had Sex with since last study visit' 0 then summarize 'Men Bottom [or Top] wo Condom since Screening' 0
    - If QSTEST 'Days Missed Tablets 7 Days BEFORE Sex [or AFTER Sex]' is missing, but 'Men Top without Condom since last visit' 0 and 'Men Bottom wo Condom since last visit' 0 then summarize 'Days Missed Tablets 7 Days BEFORE Sex [or AFTER Sex]' Not applicable
- 35) Identifying PEP versus PrEP from ARV medications:

Exclude any records that we are unable to classify as PEP or PrEP: (CMDECOD 'BLINDED INVESTIGATIONAL DRUG' or 'UNKNOWN DRUG') and CMTRT does not contain any of the following terms 'PREP' 'PRE EXPOSURE PROPHYLAXIS' 'PEP' 'POST EXPOSURE PROPHYLAXIS', 'CAB'

- a) PrEP:
  - i) either cabotegravir (CMDECOD 'NON-GILEAD INVESTIGATIONAL DRUG' or CMDECOD 'BLINDED INVESTIGATIONAL DRUG') and CMTRT contains 'CAB'
  - ii) F/TDF or generic F/TDF medication for PrEP is defined as any treatment course that includes both FTC and TDF without any other 3rd ARV agents as follows:
    - (1) F/TDF: CMDECOD 'TRUVADA' or
    - (2) Generic F/TDF: overlapping medications of CMDECOD 'EMTRICITABINE' and CMDECOD 'TENOFOVIR DF' where the medication start and end dates overlap or

(3) Potential F/TDF for PrEP: CMDECOD ("BLINDED INVESTIGATIONAL DRUG or 'UNKNOWN DRUG') and (CMTRT includes 'PREP' or 'PRE EXPOSURE PROPHYLAXIS')

and

(4) where there are no other overlapping ARV medications (excluding cabotegravir or HIV vaccine)

At any time that the medication start and end dates of F/TDF (or generic F/TDF) does not overlap with any other medication start and end dates of another ARV agent (or overlaps by 1 day), that F/TDF (or generic F/TDF) record will be considered as treatment for PrEP.

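### SAP Appendix 12 item 35(b)(ii) leaves cabotegravir off the list of drugs excluded from PEP, so a record coded 'NON-GILEAD INVESTIGATIONAL DRUG' counts as both PrEP and PEP, contrary to SAP 7.6.4

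*SAP*

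**What the plan says.** Three places in the SAP bear on how a non-study antiretroviral (ARV) record is classified.

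- **Section 7.6.4** defines PEP as "any non-study drug ARV agent other than F/TDF (or generic F/TDF), cabotegravir or HIV vaccine", taken while the participant is at risk of HIV infection. Any PEP use and the number of uses per participant are to be summarised in the FAS for the double-blind (DB) phase, and separately on and off treatment.
- **Appendix 12 item 35(a)(i)** identifies PrEP. Its first class is "either cabotegravir (CMDECOD 'NON-GILEAD INVESTIGATIONAL DRUG' or CMDECOD 'BLINDED INVESTIGATIONAL DRUG') and CMTRT contains 'CAB". Two codings of cabotegravir are thus foreseen.
- **Appendix 12 item 35(b)** identifies PEP. Part (i) takes blinded or unknown drugs "and (CMTRT includes 'PEP' or 'POST EXPOSURE PROPHYLAXIS". Part (ii) is a catch-all: "Include other known ARVs (where CMDECOD not 'BLINDED INVESTIGATIONAL DRUG' or 'UNKNOWN DRUG') excluding the following". The exclusions are numbered (1) F/TDF, (2) generic F/TDF and (3) HIV vaccine. A later paragraph turns an F/TDF record into PEP when it "overlaps with the medication start and end dates of another ARV agent (excluding cabotegravir or HIV vaccine) by more than 1 day".

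**The concern.** The body of the SAP and its programming specification disagree about one drug. Section 7.6.4 names four exclusions from PEP, and the catch-all in item 35(b)(ii) names three of them. Cabotegravir is the one missing. A programmer working from item 35 would produce a different PEP table from one working from 7.6.4.

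The omission looks unintended. Cabotegravir and HIV vaccine are set aside together in 7.6.4, in the no-overlap condition of item 35(a)(ii)(4), and in the overlap paragraph of item 35(b). Only the list under 35(b)(ii) keeps HIV vaccine and drops cabotegravir.

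At stake is a descriptive table. PEP use shows how often participants were treated after a suspected exposure while on and off study drug. Counting planned pre-exposure use there makes the table report something other than what 7.6.4 defines.

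**Working it through.** No sample size, power or alpha depends on this rule, and the plan has no figure to reproduce. The check is to pass test records through each rule as written.

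| Record | PrEP under 35(a) | PEP under 35(b) | PEP under 7.6.4 |
|---|---|---|---|
| Cabotegravir, CMDECOD 'NON-GILEAD INVESTIGATIONAL DRUG' | yes | **yes** | **no** |
| Cabotegravir, CMDECOD 'BLINDED INVESTIGATIONAL DRUG' | yes | no | no |
| F/TDF alone | yes | no | no |
| HIV vaccine | no | no | no |
| Non-study F/TAF alone | no | yes | yes |

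**Row 1.** CMTRT contains 'CAB', so 35(a)(i) gives PrEP. The CMDECOD is neither blinded nor unknown, so the record enters the catch-all in 35(b)(ii). It is not F/TDF, generic F/TDF or HIV vaccine, so nothing removes it. This is the only row where the program and 7.6.4 disagree, and the only one where a record is both PrEP and PEP.

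**Row 2.** The CMDECOD condition keeps the record out of 35(b)(ii). Part (i) needs a PEP keyword in CMTRT. The text 'PREP' does not contain 'PEP', so nothing leaks in that way.

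**Row 5.** Program and text agree, because both are catch-alls that do not mention F/TAF. This is a shared gap and not a conflict.

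**Which rows of the table move.** Under 7.6.4, a cabotegravir record that starts after the last dose and within the at-risk period enters the overall and off-treatment rows. One that starts on or before the last dose and ends after the first dose enters the on-treatment row.

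**Effect per participant.** Someone with no genuine PEP adds one to the any-use count. Someone who also had genuine PEP adds nothing to it. For the number of uses, 7.6.4 counts unique start dates and merges records that overlap or follow within one day. Cabotegravir entered as several records, each starting two or more days after the previous one ended, would therefore count as several uses.

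**Scale.** The documents give neither the number of such records nor the FAS size. As a stand-in, SAP Appendix 3 gives 5387 participants in the Safety Analysis Set.

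- One false user, overall: 1 / 5387 = 0.019%.
- One false user, per arm, assuming an even split (5387 / 2 = 2693.5): 1 / 2693.5 = 0.037%.
- Ten false users in one arm (illustrative): 10 / 2693.5 = 0.37%.

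The FAS adds HIV-test conditions to the Safety Analysis Set, so it can be no larger and the true shifts are at least this size. The off-treatment row uses a smaller denominator (participants off study drug with a later HIV test), so one record moves that percentage more.

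**The case against.** The strongest reply is that the intent is already clear. Section 7.6.4 excludes cabotegravir in plain words. Item 35 is about telling PEP from PrEP, so its 'other' ARVs could mean those not already classed as PrEP. That reading is possible, but item 35 does not state it. The condition in 35(b)(ii) contrasts it with the blinded and unknown drugs of 35(b)(i), not with 35(a). A specification should not depend on that inference.

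A second reply concerns the text itself. The first entry of the exclusion list is garbled in the available copy ('F/TDFa 1'), so a footnote may have been lost. That is an extraction fault and not an error in the plan. It does not supply the missing drug: the entries run from (1) to (3) without a gap.

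A third reply is that the effect is small and descriptive. That stands.

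A reader might also infer more than the documents support:

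- *That the program never excludes cabotegravir.* It does so for blinded-coded records and in the overlap paragraph.
- *That non-study F/TDF overlapping F/TAF would stop counting as PrEP in the 6.2.6 analysis.* Item 35 lets one F/TDF record be both PEP and PrEP where it extends past the other agent. Item 36(b) uses the start date of the non-study PrEP. If both agents start on the same day, it uses the day after the third agent ends.
- *That F/TAF used as PrEP is wrongly handled in 6.2.6.* That section covers any non-study PrEP treatment. Its examples, such as "generic Truvada, or investigational drugs like cabotegravir for PrEP", are open-ended and do not rule out F/TAF. Item 35(a) simply gives no programming rule for it.
- *That commercial F/TAF is known to distort the PEP table.* The remark "In geographic regions where F/TAF is commercially available for PrEP" concerns open-label Week 48, while the PEP summaries cover the DB phase. The documents show no such use in that phase, and F/TAF taken with a third agent may be genuine PEP.

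**Conclusion.** The point holds for one drug under one coding: as written, item 35(b)(ii) contradicts 7.6.4 and double-classifies cabotegravir coded 'NON-GILEAD INVESTIGATIONAL DRUG'. The consequence is an inflated set of FAS PEP-use summaries. The size is unknown and likely small, at most one false PEP user per affected participant.

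No efficacy conclusion changes. Cabotegravir keeps its PrEP flag under 35(a)(i), so its handling in 6.2.6 is the same, and the FAS rate ratio does not use the PEP flag.

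This rests on a literal reading of 35(b)(ii), and on cabotegravir records carrying one of the two codings that item 35(a)(i) names. The missing rule for non-study F/TAF without a third agent is a matter for clarification, not a demonstrated error. The issue is minor but worth correcting, because the rule as stated gives a wrong count.

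**What to change.** Add a fourth entry to the exclusions in item 35(b)(ii): cabotegravir, identified by CMTRT containing 'CAB'. The program then matches 7.6.4, and row 1 of the table becomes PrEP only.

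As an optional clarification, state in 7.6.4 and in item 35 how non-study F/TAF taken without a third agent is classified, and whether it counts as another ARV agent in the overlap rule. At present both catch-alls label it PEP and item 35(a) has no PrEP rule for it.

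The cost is a few words and one extra condition in the program. No new data are needed.
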